3.4.2.2 Objective Response Rate (ORR)

The objective response rate for each given group (dose level, cohort, or arm) in the Efficacy Analysis Set will be summarized according to RECIST v1.1 (and according to iRECIST), accompanied by a 2-sided exact 95% Clopper-Pearson confidence interval. ORR will be presented separately for each combination of conditions described in section [3.4.1.2](#). The summaries of ORR using confirmed vs unconfirmed CR/PR (or iCR/iPR) and for overall, by 6 weeks, by 9 weeks, by 12 weeks, and by 15 weeks after the start of study treatment will all be presented in a single table.

3.4.2.3 Progression-Free Survival (PFS)

PFS will be summarized by dose level and in total for Part A, in total for Part A-2, and by cohort and in total for Part B in the Efficacy Analysis Set for each combination of conditions described in section [3.4.1.3](#). For each combination, Kaplan-Meier estimates for the first quartile, median, and third quartile PFS will be presented along with a 95% confidence interval based on the Brookmeyer-Crowley method. Kaplan-Meier estimates of the PFS at 3 months, 6 months, 9 months, and 12 months will be presented along with associated 95% Greenwood confidence intervals.

3.4.2.4 Overall Survival (OS)

OS will be summarized by dose level and in total for Part A, in total for Part A-2, and by cohort and in total for Part B in the Efficacy Analysis Set. Kaplan-Meier estimates for the first quartile, median, and third quartile OS will be presented along with a 95% confidence interval based on the Brookmeyer-Crowley method. Kaplan-Meier estimates of the OS rate at 6 months, 12 months, 18 months, and 24 months will be presented along with associated 95% Greenwood confidence intervals.

Kaplan-Meier curves will be presented for OS.

Survival status assessments and death details will be listed by patient.

3.5 Pharmacokinetic Assessment

Pharmacokinetic analysis will be performed for patients in the Pharmacokinetic Set.

3.5.1 Sample Collections for Pharmacokinetic Analysis

Pharmacokinetic blood sampling timepoints for determination of serum concentrations of NM21-1480 (2-week Dosing Interval) during Part A, Part A-2 and Part B of the study

VISIT	DAY	PK SAMPLING TIME
Cycle 1	1	(Pre-dose) 0 EOI ± 5 min [#] 4 h ± 10 min* 8 h ± 1 h*
	2	24 h ± 2 h*
	3	48 h ± 4 h*
	5	96 h ± 12 h*
	8	168 h ± 24 h
	15 ± 2	(Pre-dose) 0
Cycle 2	1 ± 2	(Pre-dose) 0
	8 ± 2	168 h ± 48 h
	15 ± 2	(Pre-dose) 0
Cycle 3	1 ± 3	(Pre-dose) 0 EOI ± 5 min [#] 4 h ± 10 min*

		8 h ± 1 h*
2		24 h ± 2 h*
3		48 h ± 4 h*
5		96 h ± 12 h*
8		168 h ± 24 h
15 ± 3		336 h ± 48 h*
Every subsequent even cycle	8 ± 3	168 h ± 48 h
Every subsequent odd cycle	1 ± 3	(Pre-dose) 0
First follow up visit		Anytime

* EOI: End of Infusion sample is taken immediately prior to stopping the infusion from the counter arm of the site of injection. All subsequent timepoints indicated for PK blood draws refer to hours *after* EOI

* Optional sampling point for Part B. Sites are not required to collect these optional PK samples in Part B. These sampling timepoints are however mandatory in Part A-2

3.5.2 Handling Missing or Below the Lower Limit of Quantification Data

For PK concentration data, if the actual sampling time is missing, but a valid concentration value has been measured, the concentration value will be flagged, and the scheduled nominal time point may be used for the calculation of PK parameters.

In cases of missing pre-dose concentrations prior to the first dose of Cycle 1, the missing concentration value may be imputed as zero. If missing pre-dose concentrations of Cycle 3, the pre-dose of Cycle 4 (or any cycle after Cycle 3) may be used as pre-dose concentration values. For the other cases, the missing data will not be imputed.

For the individual concentration and PK parameter calculation for Part A and A-2 by dose level and cycle and Part B by cohort and cycle, the following rules will be applied:

- If one or more below the limit of quantitation (BLQ) values occur before the first measurable concentration, they will be assigned a value of zero.
- If BLQ values occur between measurable concentrations in a profile, the BLQ should be omitted (set to missing).
- If BLQ values occur after the last measurable concentration in a profile, the BLQ should be omitted (set to missing).

For the concentration summary of NM21-1480 and mean (±SD) concentration plot preparation for Part A and A-2 by dose level and cycle and Part B by cohort and cycle, the following rules will be applied:

- Mean concentration at any individual time point will only be calculated if at least half of the patients have valid values (i.e. quantifiable and not missing) at this time point for each dose level, cohort and cycle.
- In cases where a mean value is not calculated due to the above criterion not being met, the value will be set to missing.
- BLQ values will be set to zero.
- The value of zero will be excluded from the calculation of GM and GM CV%

3.5.3 Pharmacokinetics Concentrations

Individual serum concentrations of NM21-1480 will be summarized by dose level and cycle (combined for Part A and A-2) and Part B by cohort and cycle at each nominal time point for the PK set descriptively. Individual serum concentrations will also be listed for the PK set.

Individual serum concentration (ie., Spaghetti plots) will be plotted by dose level, cohort and cycle for Cycle 1 and Cycle 3 on a linear and semi-logarithmic scale against actual sampling time points relative to dosing time. Mean (\pm SD) concentration will be plotted on a linear and semi-logarithmic scale against nominal time points by dose level, cohort and cycle, when available for Part A, Part A-2, and Part B. LLOQ will be plotted as a reference line in both instances.

Mean (\pm SD) and Spaghetti plots for NM21-1480 serum concentrations at C_{168h} and C_{trough} will be plotted for Part A and A-2 by dose level and cycle and Part B by cohort and cycle.

Actual sampling times that are outside the sampling time windows may be excluded at the discretion of the clinical pharmacologist from concentration summary and mean concentration plotting but will still be used in the calculations of PK parameters and individual concentration plotting.

The following descriptive statistics will be used for all summary data: n, arithmetic mean, geometric mean, standard deviation, geometric standard deviation, coefficient of variation (CV%), geometric CV% (calculated as: $gCV\% = \text{SQRT}(e^{s^2}-1)*100$; where s is the standard deviation of the log-transformed values), minimum, maximum and median.

The following rules will be followed with regards to the number of decimal places and presentation of data in the tables and listings of concentration data:

- Source data shall be used in all derived PK concentrations without prior rounding.
- The mean, standard deviation (SD), geometric mean and median will be tabulated to one more significant digit compared to the source data, but with a maximum of four significant digits.
- Minimum and maximum values will be tabulated to the same precision as the source data, but with a maximum of four significant digits.
- Geometric coefficient of variation (%CV) and coefficient of variation (%CV) will be presented to one decimal place.

3.5.4 Pharmacokinetics Parameters

The following serum PK parameters of NM21-1480 will be determined using WinNonlin v8.3 non-compartmental methods as appropriate for all parts (A, A-2 and B) for all patients for whom parameters can be calculated:

Parameters	Description and Calculation	Cycle
C_{max}	Maximum serum concentration; determined directly from the concentration time profile; if the maximum serum concentration occurs at more than one time point, C_{max} is defined as the first maximum value	Cycle 1, Cycle 3

C_{min}	Minimum serum concentration over the dosing interval	Cycle 1, Cycle 3
T_{max}	Time to C_{max} ; If the maximum value occurs at more than one time point, T_{max} is defined as the first time point with this value	Cycle 1, Cycle 3
λ_z	Apparent first-order terminal elimination rate constant calculated from a semi-log plot of the serum concentration versus time curve. The parameter will be calculated by linear least-squares regression analysis using points in the terminal log-linear phase.	Cycle 1, Cycle 3
$t_{1/2}$	Apparent first-order terminal elimination half-life; calculated as $\ln(2)/\lambda_z$	Cycle 1, Cycle 3
AUC_{0-t}	Area under the serum concentration vs time curve (AUC) from predose (time 0) to the last quantifiable serum concentration (C_{last})	Cycle 1, Cycle 3
AUC_{tau}	AUC over the dosing interval	Cycle 1, Cycle 3
AUC_{0-inf}	AUC from time 0 to infinity; calculated as $(AUC_{0-t} + C_{last}/\lambda_z)$	Cycle 1
$AUC_{%extrap}$	Percent of AUC_{0-inf} extrapolated, represented as $(1 - AUC_{0-t}/AUC_{inf}) * 100$	Cycle 1, Cycle 3
CL	Total serum clearance after IV administration; calculated as Dose/ AUC_{inf}	Cycle 1
CL _{ss}	Total serum clearance after IV administration; calculated as Dose/ AUC_{tau}	Cycle 3
Vd	Volume of distribution during terminal elimination phase after IV administration; calculated as Dose/ $[\lambda_z * AUC_{inf}]$	Cycle 1
Vd _{ss}	Volume of distribution during terminal elimination phase after IV administration; calculated as Dose/ $[\lambda_z * AUC_{tau}]$	Cycle 3
Accumulation Index (AR _{Cmax})	Accumulation ratios assessment of C_{max} ; calculated as C_{max} in Cycle 3 divided by C_{max} in Cycle 1	Cycle 3

Accumulation Index (AR _{C_{min}})	Accumulation ratios assessment of C _{min} ; calculated as C _{min} in Cycle 3 divided by C _{min} in Cycle 1	Cycle 3
Accumulation Index (AR _{AUC})	Accumulation ratios assessment of AUC; calculated as AUC _{tau} in Cycle 3 divided by AUC _{tau} in Cycle 1	Cycle 3

Actual collection times will be used in PK parameter calculations. The Linear-Log Trapezoidal method (equivalent to the Linear Up/Log Down option in WinNonlin) will be used in the computation of all AUC values. In order to estimate the apparent first-order terminal elimination constant, λ_z , linear regression of concentration in logarithm scale vs. time will be performed using at least 3 data points post C_{max}. Uniform weighting will be selected to perform the regression analysis to estimate λ_z . The constant λ_z will not be assigned if one of the following occurs:

1. The terminal elimination phase is not linear (as it appears on a semi-logarithmic scale).
2. The terminal elimination rate constant indicates a positive slope ($\lambda_z > 0$).
3. T_{max} is one of the three last data points.

The constant λ_z and its derived parameters will be flagged and included in the statistical analysis if one of the following occurs:

1. The adjusted regression coefficient (R²) is less than 0.8.
2. The AUC_{%extrap} exceeds 20%.

No value for λ_z , AUC_{0-inf}, AUC_{%extrap}, CL, CLss, Vz, Vzss or t_{1/2} will be reported for cases that do not exhibit an acceptable terminal log-linear phase in the concentration-time profile.

No PK parameters will be calculated for patients with 2 or fewer detectable concentrations in their PK profile.

PK parameters will be listed per patient and summarized by dose level and cycle (combined for Part A and A-2) and by cohort and cycle (Part B). The summaries of PK parameters will use following descriptive statistics: n, arithmetic mean, standard deviation, geometric mean, geometric standard deviation, 95% CI geometric mean, coefficient of variation (CV%), geometric CV% (calculated as: gCV% = $\sqrt{e^{s^2}-1} * 100$; where s is the standard deviation of the log-transformed values), minimum, maximum and median. Tmax will include median, minimum and maximum. No descriptive statistics will be determined when fewer than three individual PK parameters are available.

All available data will be presented in patient data listings which will be sorted by patient and visit date as applicable.

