		PK ^{a,b, j}	ADA ^j	IPT	sPD-L1/ sCD137	Cytokines	RO	ctDNA ^k	PD-L1 IHC	TMB, TCRseq, & MSI by DNA Analysis	mRNA/ IF	DNA, mRNA, IHC ^h
Visit name / Study day	Time Point	Serum	Serum	Whole Blood	Serum	Serum	Whole Blood	Whole Blood	Biopsy (FFPE)	Biopsy (FFPE)	Biopsy (FFPE) ^c	Mandato ry Biopsy ^h
Cycle 2, Day 1 / Study Day 29 ± 2	Pre-dose	x ^g	x ^g	x ^g	x ^g	x ^g	x ^g	x ^k			x	
Cycle 2, Day 8 / Study Day 36 ± 2	168 h ± 48 h	x ^g	x ^g	x ^g	x ^g	x ^g	x ^g					
Cycle 2, Day 15 / Study Day 43 ± 2	Pre-dose	x ^g	x ^g		x ^g	x ^g		x ^k				
Cycle 3, Day 1 / Study Day 57 ± 3	Pre-dose	x ^g	x ^g	x ^g	x ^g	x ^g	x ^g	x ^k			x	
	EOI ^f ± 5 min	x ^g										
	4 h ± 10 min	x ^d										
	8 h ± 1 h	x ^d										
Cycle 3, Day 2 / Study Day 58	24 h ± 2 h	x ^d				x ^d						
Cycle 3, Day 3 / Study Day 59	48 h ± 4 h	x ^d										
Cycle 3, Day 5 / Study Day 61	96 h ± 12 h	x ^d										
Cycle 3, Day 8 / Study Day 64	168 h ± 24 h	x ^g				x ^g						
Cycle 3, Day 15 / Study Day 71 ± 3	336 h ± 48 h	x ^d						x ^k				

		PK ^{a,b, j}	ADA ^j	IPT	sPD-L1/ sCD137	Cytokines	RO	ctDNA ^k	PD-L1 IHC	TMB, TCRseq, & MSI by DNA Analysis	mRNA/ IF	DNA, mRNA, IHC ^h
Visit name / Study day	Time Point	Serum	Serum	Whole Blood	Serum	Serum	Whole Blood	Whole Blood	Biopsy (FFPE)	Biopsy (FFPE)	Biopsy (FFPE) ^c	Mandato ry Biopsy ^h
All subsequent even-numbered cycles, Days 1 and 15 / Study Days e.g., 85 ± 3, 99 ± 3, 141 ± 3, 155 ± 3, etc.								x ^k				
All subsequent even-numbered cycles, Day 8 / Study Days e.g., 92 ± 3, 148 ± 3, 204 ± 3, etc.	168 h ± 48 h	x ^g	x ^g	x ^g	x ^g	x ^g	x ^g					
All subsequent odd-numbered cycles, Day 1 / Study Days 113 ± 3, 169 ± 3, etc.	Pre-dose	x ^g	x ^g	x ^d	x ^d	x ^d	x ^d	x ^k		x		
All subsequent odd-numbered cycles, Day 15 / Study Days e.g., 127 ± 3, 183 ± 3, etc.								x ^k				
Follow-up Period	--	x (FU1 only)	x (FU1 only)					x ^k (FU1, FU2, and FU3)				

Abbreviations: ADA = Anti-drug antibodies; D = Dose (study drug administration); DNA = Deoxyribonucleic acid; EOI = End of infusion; FFPE = Formalin-fixed paraffin-embedded; h = Hour; IHC = Immunohistochemistry; IPT = Immunophenotyping; TMB = Tumor mutational burden; MSI = Microsatellite instability; IF = Immunofluorescence;

PK = Pharmacokinetics; PD-L1 = Programmed death-ligand 1; mRNA = Messenger Ribonucleic acid; RO = Receptor occupancy; TCRseq = T-cell receptor sequencing; TMB = Tumor mutational burden

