*Assessment of IPT, sPD-L1, sCD137, cytokine panel, RO, PD-L1 IHC, TMB, TCRseq, MSI and mRNA/IF may be adjusted for Part B, following availability of Part A data; conduct of RO assay (for Part A and B) will be dependent on availability of a suitable assay.

- a. Serial PK samples will be collected from all the patients enrolled in Part A and A-2. For the patients in Part B serial PK is optional except for the mandatory pre-dose, EOI and 168 ± 24 h sampling timepoints (see footnote "g").
- b. If a patient permanently discontinues study drug treatment, or is not receiving an infusion at a given visit, a single PK sample will be taken at that visit.
- c. Optional biopsy material for patients enrolled in Part A and A-2 from as many cycles as possible, and Follow-up period. For patients in Part B, a single post treatment biopsy material collection is considered mandatory per footnote "r" in [Table 7-1](#), i.e., for patients presenting with at least stable disease during treatment with NM21-1480.
- d. Optional sampling point for Part B. Sites are not required to collect these optional PK samples in Part B. These sampling timepoints are however mandatory in Part A and Part A-2. For sampling timepoints considered mandatory in Part B at all sites, see also footnote "g".
- e. EOI: End of Infusion. This sample should be taken immediately prior to stopping the infusion from the counter arm of the site of injection. All subsequent timepoints indicated for PK blood draws refer to hours *after* EOI.
- f. For FU visits: PK and ADA sample will be taken at Follow-up Visit 1 only.
- g. Mandatory sample for all patients in Part A, Part A-2 and Part B (unless drawing is not considered clinically feasible due to the condition of the patient).
- h. Only applicable for mCRC patients enrolled to Cohort B8. For specifics on sample acquisition please refer to specialty lab manual.
- i. Reference is made to footnote gg in Table 7-1 for timing of these mandatory on-treatment biopsies for mCRC patients enrolled to Cohort B8.
- j. Not applicable to patients in Cohort B5 randomized to standard-of-care anti-PD1 therapy only.
- k. Only applicable for mCRC patients enrolled to Cohort B8.

Table 7-4 Backup Pharmacokinetics, Anti-Drug Antibody, and Pharmacodynamic Blood Sampling Schedule (3-week Dosing Interval: APPLICABLE TO PART A-2 AND B ONLY IN CASE OF A POTENTIAL FUTURE SMC DECISION TO PROLONG DOSING INTERVAL#)

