10.6.10 Analysis of Pharmacokinetics Endpoints and Anti-Drug Antibody

Pharmacokinetic parameters such as Cmax, Cmin, Tmax, λ_z , $t_{1/2}$, Tmax, AU C_{tau} , CL, apparent Vd, and accumulation index will be derived from serum concentration versus time data for patients with serial PK samples. Data obtained from patients with serial sampling and limited sampling will eventually be combined with data from other studies for population PK analysis but reported separately.

A listing will be generated of all available immunogenicity data, comprising all numeric titer values. Additionally, a listing of immunogenicity data from those patients with at least 1 positive ADA assessment (titer value greater than 2-fold of baseline titer) at any time point will be provided by dose regimen. The frequency of patients with at least 1 positive ADA assessment (titer value greater than 2-fold of baseline titer), and frequency of patients who develop ADA after a negative baseline assessment (i.e., titer value equal to 1), and frequency of patients who develop ADAs after a baseline titer assessment greater than 1, will be provided by dose. In addition, the frequency of patients who do not develop ADAs after treatment following either a negative baseline assessment (i.e., titer value equal to 1), or a baseline titer greater than 1 will be provided by dose. Treatment-induced, treatment-enhanced and treatment-unaffected ADA patients will be summarized. In addition, to examine the potential relationship between immunogenicity and safety, the frequency and type of AEs may be examined by overall immunogenicity status.

Serum concentrations of NM21-1480 will be determined using validated bioanalytical methods. Serum concentration-time profiles for NM21-1480 will be generated. Descriptive summaries for NM21-1480 concentrations will be presented by dose and formulation.

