2.8.2 Secondary Endpoints

- Disease Control Rate (DCR)
- DOR
- TTR
- PFS
- OS
- BOR, DCR, ORR, DOR, PFS as per iRECIST
- PK parameters
 - AUC_{tau}
 - $AUC_{0-\infty}$ (first dose only)
 - AUC_{0-t}
 - C_{\max}
 - C_{\min}
 - $t_{1/2}$
 - T_{\max}
 - λz
 - CL
 - CL_{ss}
 - V_d
 - Vd_{ss}
- Frequency of specific anti-drug antibodies to NM21-1480

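### Part B patients with only the mandatory PK samples get no terminal-phase parameters, and their AUC0-t is averaged over unequal time spans across cycles and patients

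*SAP*

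**What the plan says.** SAP 2.8.2 lists 12 "PK parameters" as secondary endpoints for Part B: AUCtau, AUC0-inf, AUC0-t, Cmax, Cmin, t1/2, Tmax, lambda-z, CL, CLss, Vd and Vdss. SAP 3.5.4 determines them by "non-compartmental methods as appropriate for all parts (A, A-2 and B) for all patients for whom parameters can be calculated".

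On sampling, protocol Table 7-3 (footnote a) states: "For the patients in Part B serial PK is optional except for the mandatory pre-dose, EOI and 168 ± 24 h sampling timepoints". SAP 3.5.1 marks the 4, 8, 24, 48 and 96 h samples, and the 336 h sample in Cycle 3, with the note: "Optional sampling point for Part B. Sites are not required to collect these optional PK samples in Part B". The Cycle 3 336 h sample is the row "Cycle 3, Day 15 / Study Day 71 ± 3" in Table 7-3. By contrast, the Cycle 1 Day 15 pre-dose sample is mandatory.

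SAP 3.5.4 also sets the derivation rules:

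- For lambda-z, "linear regression of concentration in logarithm scale vs. time will be performed using at least 3 data points" after Cmax.
- Lambda-z is not assigned if Tmax is one of the last three points.
- Without an acceptable terminal phase, lambda-z and the quantities that depend on it are not reported.
- A profile with two or fewer detectable concentrations gives no parameters at all.
- AUC0-t runs to the last quantifiable concentration, with no common end time.
- Part B summaries are by cohort and cycle, with no split by sampling density.

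Protocol 10.6.10 is narrower. It says the parameters "will be derived from serum concentration versus time data for patients with serial PK samples". SAP section 6 does not list this difference.

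**The concern.** The SAP's own rules pull apart on sparse profiles. They block every terminal-phase quantity but let AUC0-t through. The AUC0-t that survives covers a full dosing interval in Cycle 1 and half of one in Cycle 3. Within Cycle 3 it also mixes patients who stop at 168 h with patients who reach 336 h. The cohort table would then show a cycle contrast that depends partly on which sites took optional samples.

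The question at stake is whether exposure is maintained. The protocol's rationale for studying 800 mg is that the loss of exposure seen with anti-drug antibodies at 24 to 240 mg was not seen at 800 mg, and section 5.3.3 asks for continued evaluation of long-term exposure. An AUC summary that can suggest loss, or hide accumulation, because of where sampling stopped does not help to answer it.

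**Working it through.** The plan gives no figure to reproduce here. The check has two parts.

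**1. Which parameters survive on mandatory samples**

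This takes Cmax at end of infusion (EOI).

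| | Cycle 1 | Cycle 3 |
|---|---|---|
| Mandatory samples | pre-dose, EOI, 168 h, Day 15 pre-dose (about 336 h) | pre-dose, EOI, 168 h |
| Points after Cmax (SAP minimum 3) | 2 | 1 |
| Tmax among last three points | yes | yes |
| Detectable values (more than 2 needed) | 3 (pre-dose is before any drug) | 3 |

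- Lambda-z fails both rules in both cycles. With it go t1/2, AUC0-inf, CL, CLss, Vd and Vdss: 7 of the SAP's 12 parameters. (SAP 3.5.4 writes Vz and Vzss for Vd and Vdss in its suppression rule.)
- Cycle 3 AUCtau is lost because sampling stops at 168 h of a 336 h interval and there is no lambda-z to extrapolate with. The AUC accumulation ratio, which uses AUCtau, is lost too.
- AUC0-t passes the detectable-value filter in both cycles. The Cycle 1 result assumes that the Day 15 pre-dose sample belongs to the Cycle 1 profile, which the SAP does not state. If it does not belong, Cycle 1 has 2 detectable values and no parameter is calculated.

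**2. What the unequal spans do to AUC0-t**

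Inputs:

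- dosing every 14 days (protocol 7.1);
- Cycle 3 Day 1 is the fifth dose (Days 1, 15, 29, 43, 57);
- 60 to 90 minute infusion (protocol 8.1), taken as 1.25 h;
- one-compartment kinetics (assumed);
- half-life h in days, varied. The only human value in the documents is the roughly 2-week prediction in protocol 5.1.2.

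For a bolus dose the result has a closed form:

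- Share of the Cycle 3 interval AUC kept at 168 h: T = (1 − 2^(−7/h)) / (1 − 2^(−14/h)).
- True Cycle 3/Cycle 1 ratio over full intervals: R = 1 + q + q² + q³ + q⁴, with q = 2^(−14/h).
- Apparent ratio, 168 h in Cycle 3 over 336 h in Cycle 1: T × R.

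At h = 14: T = 0.586, R = 1 + 0.5 + 0.25 + 0.125 + 0.0625 = 1.94, and T × R = 1.14.

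With the infusion and the SAP's linear-up/log-down trapezoid:

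| Half-life (days) | Share kept | True ratio | Apparent AUC0-t ratio |
|---|---|---|---|
| 3 | 0.84 | 1.04 | 0.87 |
| 5 | 0.73 | 1.17 | 0.85 |
| 7 | 0.67 | 1.33 | 0.89 |
| 10 | 0.62 | 1.60 | 0.995 |
| 14 | 0.59 | 1.94 | 1.14 |

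The apparent ratio crosses 1 at a half-life of about 10.1 days.

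The ratio of cohort means also moves with the share of patients who have the optional 336 h sample, even if all patients are kinetically identical. It equals share × true ratio + (1 − share) × apparent ratio:

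| Share with 336 h sample | Half-life 5 days | Half-life 14 days |
|---|---|---|
| 0 | 0.85 | 1.14 |
| 20% | 0.91 | 1.30 |
| 50% | 1.01 | 1.54 |
| 100% | 1.17 | 1.94 |

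**The case against.** The case on the other side has real force, and most of it limits the point rather than removing it.

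- **Blank, not wrong.** Derivation is confined to patients for whom parameters can be calculated, and the lambda-z rules screen out sparse profiles. The seven parameters would be missing or rest on patients with optional samples. This stands, and for those parameters it largely reproduces the protocol's serial-sample limit. It does not cover AUC0-t, which the filter admits.
- **No AUC0-t ratio is planned.** The planned AUC accumulation ratio uses AUCtau and would be missing, not falsely low. SAP 3.5.3 already plans C168h and trough plots and concentration summaries at each nominal time. This stands. But AUC0-t is tabulated for both cycles, and with the formal ratio absent, readers are likely to compare the two.
- **Limited consequence.** The 800 mg choice was made on Part A data, where serial sampling was mandatory. Part B closed early with 5, 5 and 10 patients, and no hypothesis tests are planned. AUC0-t is not among the protocol's nine listed PK parameters. The Cmax accumulation ratio remains computable. All of this stands.

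A reader might go further in two ways that the documents do not support. One is to infer that Cycle 3 exposure will always look lower than Cycle 1. That ignores carry-over: at the predicted 14-day half-life the apparent ratio is 1.14, a rise. The other is to infer that the SAP breaches a protocol requirement to tabulate serial and limited sampling separately. The sentence in protocol 10.6.10 concerns pooling with other studies for population PK, and its natural reading is that the population analysis is reported separately. The serial-sample limit in the same section is explicit, and that is the departure to record.

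**Conclusion.** The point holds for Part B patients with mandatory samples only. Seven of the 12 SAP parameters, Cycle 3 AUCtau and the AUC accumulation ratio cannot be derived. AUC0-t covers about 336 h in Cycle 1 and 168 h in Cycle 3, and is averaged within cohort and cycle with patients sampled to 336 h.

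Truncation keeps 73% (half-life 5 days) to 59% (14 days) of the Cycle 3 interval AUC. The direction of the resulting error depends on the half-life. At 5 to 7 days it shows a false loss (true 1.17 to 1.33, apparent 0.85 to 0.89). At 14 days it hides accumulation (true 1.94, apparent 1.14). Part A's finding of no substantial accumulation points towards the shorter half-lives, and the 2-week prediction towards the longer; the documents do not settle which applies.

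The counts follow directly from the SAP's rules, given Cmax at EOI. The ratios rest on one-compartment kinetics, the assumed half-lives, and counting the Day 15 pre-dose sample in the Cycle 1 profile. The documents do not say how many of the 20 Part B patients lack the optional samples, so the effect on the actual tables cannot be sized. It is worth correcting because it touches a listed secondary endpoint and costs almost nothing.

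**What to change.** Change the SAP only:

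1. Summarise AUC over a common span in both cycles: AUC0-168h for everyone, or 0 to 336 h only where a 336 h sample exists in that cycle.
2. State that the Cycle 1 Day 15 pre-dose sample is the 336 h point of the Cycle 1 profile.
3. Limit the terminal-phase parameters and interval AUC to serially sampled patients, as in protocol 10.6.10, and show n in each cell.
4. Show sparsely sampled patients by EOI, C168h and trough concentrations. SAP 3.5.3 already produces these, so only the split by sampling type is new.
5. If the wider derivation in 3.5.4 is kept, list it in section 6 as a departure from the protocol's serial-sample limit.

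The cost is wording and a few table changes. The downside is fewer Part B patients in the non-compartmental tables, in cohorts that are already small.

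Making the Cycle 3 Day 15 sample mandatory cannot help this trial, which has closed. If the schedule is reused, that row should be mandatory and labelled pre-dose, as for Cycle 1 Day 15. It falls on a dosing visit, and its ±48 h window would admit a draw after that day's infusion.
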